1.4 Preliminary Data

Using community based participatory research methods, we conducted interviews, focus groups, and user testing with 50 low-income, Latino parents and engaged other stakeholders including health professionals, early educators, and community leaders to understand shared reading in the broader context of parenting. The themes we identified aligned with the Health Belief Model, and uncovered targets to enhance ROR. During interviews, low-income, Latino parents identified benefits of shared reading; they viewed it as an important activity that could enhance their children's future. Parents viewed their children as susceptible to language delays and doing poorly in school, citing their own missed educational opportunities; they saw shared reading as an opportunity to avoid these difficulties. These themes align well with the constructs of perceived susceptibility and benefits from the Health Belief Model.

Despite these beliefs, we found a gap between intention and behavior – almost half of the parents we later surveyed (77% Spanish-speaking) reported no shared reading in the last week (79/160) and 85% read ≤ 3 times. Parents intended to engage in shared reading but did not. Once at home other responsibilities (e.g., caring for other children, chores) took their attention away from opportunities for shared reading. One potential reason is that ROR activities are limited to the office, and thus parents do not receive any cues to action in their home environment when needed. Therefore, we designed an

outreach strategy with our stakeholder partners that consisted of text messages to provide a cue to action when parents were at home with their children to overcome this intention to behavior gap. The message content directly addressed beliefs about child development and shared reading that parents reported during interviews and provided reminders and reinforcement. We sought extensive feedback from stakeholders and assessed the acceptability of the messages through focus groups and user testing. We then conducted a RCT comparing the standard ROR to ROR plus texts. We found that ROR plus text improved the home literacy environment compared to ROR only at the 6-month post-assessment. However, while positive; we found the effects of text messages beyond ROR on the home literacy environment and shared reading more specifically are only partial and the effects on child outcomes beyond ROR are not known.

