Linkage to services			✓	- Completed referral	Connecting NJ data Parent-reported resources

Arm 1: Reach Out and Read (ROR) only; Arm 2: ROR + texts; Arm 3 ROR + texts + Connecting NJ

B. Dependent Variables or Outcome Measures

- Language acquisition will be assessed using the Expressive One-Word Picture Vocabulary Test - Fourth Edition (EOWPVT-4) Spanish-Bilingual - Complete. This multiple-choice format test consists of 190 items presented in developmental sequence; age-related starting points and cut-off points ensure that only a subset of items is administered.
- MacArthur Bates Communicative Development Inventories (CDIs)¹⁶ are standardized, parent-reported check-lists that assess language and communication in children ages 8-37 months. These checklists focus on children's' nonverbal gestures and early signs of language comprehension, and they are available in English and Spanish.
- Social-emotional skill acquisition will be measured with the Devereux Early Childhood Assessment (DECA),¹⁷ a validated 33-item parent report of socio-emotional problems that is available in both English and Spanish.
- Shared reading and parent responsiveness will be assessed with the StimQ.¹⁸ The StimQ is a parent-reported measure of the cognitive home environment for children that includes domains on shared reading (Reading scale) and responsiveness (Parental Verbal Responsiveness scale). We added 8 questions to supplement this survey. We also will implement the DialogPR¹⁹, a parent report of shared reading quality. We will also conduct observations of parent-child interactions during a shared reading and a play activity to assess parenting strategies around reading. We plan to video- and audio-record these sessions using a video-conferencing software, after consenting the participant to this process. The Research Assistant will observe the parent-child interactions and assess responsiveness and other characteristics of the exchange.

The observations will be done virtually, over the computer or phone, and recorded using a video-conferencing software, so that our study team can: (1) code reading strategies and interactions and (2) have a supervising researcher code the same interactions to strengthen the reliability of the coding.

- Positive and negative parenting behaviors will be assessed through The Parenting Your Infant or Parenting Your Toddler surveys, derived from the Parenting Your Child²⁰ measure. The Parent

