In the event we are able to visit clinics in person after COVID-19 restrictions have been lifted, trained bilingual research assistants will work closely with clinical staff to identify potential participants.

All study documents including recruitment flyers (see attached) will be written in accessible language with low literacy burden in consultation with our clinical expert advisory committee and parents. Study documents will be translated into Spanish using forward back translation and will be reviewed by bilingual members of the study team.

Interview participants will be recommended to us from the clinics or from our advisory committee. We will send them the information sheet about the study and ask if they would like to participate in the interview.

C. Subject Screening

Trained research assistants will screen participants for eligibility using a checklist (see attached)

- **Inclusion Criteria**

The inclusion criteria for parent participants in all aims will be: (1) primary caregiver of a child age 6 months to 12 months, (2) identifies as Latino/a/x, (3) primary language English or Spanish, (4) cell phone ownership, (5) age 18 years or older (6) willing to receive text messages, and (7) willing to accept randomization. Inclusion criteria for children will be age 6-12 months.

We will also be interviewing clinicians from our study sites as part of our process evaluation. All clinicians who administer ROR will be eligible to participate in interviews. We will also ask an office manager or administrator to complete a very short practice survey.

ROR experts and others will be recommended based on experience and knowledge of ROR implementation.

- **Exclusion Criteria**

Individuals unable to provide informed consent will be excluded. Individuals who plan on changing their pediatric clinic within the study (i.e., because they are moving out of the country) will be excluded. Children with multiple congenital anomalies or genetic disorders and previously identified developmental delays will be excluded.

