6.0 Data Management Plan

6.1 Data Analysis

1. Enrollment: We will recruit 630 parent-child dyads (210 per arm) over a 24-month time period. We expect that 80% of the 630 enrolled parent-child dyads will complete the study, leaving 525 parent-child dyads (175 in each arm).

2. Sample size and power:

630 parent-child dyads (210 per arm) will be sufficient to achieve 80% power to detect a 0.3 standard deviation (SD) difference in the primary endpoints language scores on the EOWPVT-4 and social-emotional skill scores on the DECA at 18 months between (1) ROR + texts and ROR only and (2) ROR + texts + Central Intake and ROR + texts, assuming approximately 20% attrition based on our past work²⁹ and using 0.05 significance level. An effect size of 0.3 SD difference would be clinically meaningful since it would be associated with a detectable difference in later cognitive functioning, based on work from a prospective cohort.³⁰ The proposed sample size will provide 99.9% power to detect a 0.6 SD difference between the community resource arm and ROR only, based on the expected additive effects of the text message and enhanced access to poverty-reducing resources.

3. Analysis:

Distributions of baseline characteristics will be summarized overall as well as by randomization group. We will assess the distribution of outcome data using descriptive statistics to check the assumption of normality for continuous variables. We will estimate mean outcomes for each treatment group as well as mean differences between groups (with confidence intervals). If any continuous outcomes are skewed, we attempt log-transformation or other to stabilize the variance and normalize distributions.

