For aim 1, analysis will follow the intention to treat principle, in which participants are analyzed based on their group assignment, whether or not they receive the strategies for all outcomes. Because of the multiple, potentially highly correlated outcomes, the step-down minP method (a re-sampling approach), will be used to assess the effects of treatment³¹ across outcomes and timepoints within each domain (language development, social-emotional development, and parenting). We will use ANOVAs to evaluate treatment effects on adjusted outcomes. Specifically, for outcomes with more than one post-treatment timepoint and a baseline assessment, we will calculate individual- and baseline-adjusted outcomes from linear models with random individual-specific intercepts (random effect) and treatment and baseline as fixed effects. Then, the adjusted outcome is estimated as the observed outcome minus the best linear unbiased predictor (BLUP) of individual-specific intercept and baseline contribution. For outcomes with one post-treatment timepoint and a baseline assessment, a baseline-adjusted outcome

will be estimated from ANCOVA results as the observed outcome minus the estimated intercept and baseline contribution. The differences in means from ANOVAs focused on these adjusted outcomes will estimate treatment effects. For secondary outcomes, statistical significance will be set at $p < 0.05$ without adjustment for multiple comparisons. For language outcomes, we will adjust for child age and sex in sensitivity analyses.

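### The primary EOWPVT-4 analysis has no baseline score and no stated covariate, so the family's language, known at enrollment, is left unused and some precision may be lost

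*Combined protocol and SAP*

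**What the plan says.** Section 4.1 C, third inclusion criterion: "3) primary language English or Spanish". Section 1.9 A lists a questionnaire on demographics and language use among the enrollment instruments.

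Section 6.1, item 2, names the EOWPVT-4 and the DECA at 18 months as the primary endpoints for the power statement. The data-points table in section 1.3 B schedules the EOWPVT-4 at 18 months only, and section 1.9 A names a single Spanish-Bilingual edition for all children. The CDI is scheduled at enrollment, 9 months and 18 months, and section 1.6 B says of its checklists that "they are available in English and Spanish".

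Section 6.1, item 3, describes two kinds of adjusted outcome:
- With a baseline and several follow-ups, the baseline contribution and the predicted individual intercept are subtracted.
- With a baseline and one follow-up, the ANCOVA intercept and baseline contribution are subtracted.

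The EOWPVT-4 has no baseline and fits neither. The only further adjustment is "For language outcomes, we will adjust for child age and sex in sensitivity analyses". Language appears in no Aim 1 model.

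**The concern.** A vocabulary score in children from two language backgrounds is an obvious place for language to predict the outcome. A baseline score would carry much of that information, but the EOWPVT-4 has none. Any mean difference between English- and Spanish-primary families therefore counts as residual noise in the primary comparison.

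What is at stake is interval width and a little power on one primary endpoint. The plan has no large reserve there: section 6.1 puts the sample at "sufficient to achieve 80% power to detect a 0.3 standard deviation (SD) difference" between adjacent arms. The variable needed is already in hand, because primary language must be established to settle eligibility.

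**Working it through.** **Inputs from the documents.** Section 6.1: "We will recruit 630 parent-child dyads (210 per arm) over a 24-month time period"; 175 completers per arm; a 0.3 SD difference; "using 0.05 significance level" (sidedness not stated, two-sided assumed).

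**The plan's own figure.** With total SD = 1, power = Φ(0.3 × √(n/2) − 1.96). At n = 175: 0.3 × √87.5 = 2.806; 2.806 − 1.96 = 0.846; Φ = 0.801. The noncentral t gives 0.799. The stated 80% is reproduced, with no covariate in the model.

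**Assumed inputs.**
- Share of Spanish-speaking families p = 0.77. Section 1.4 gives this for an earlier survey of 160 parents: "almost half of the parents we later surveyed (77% Spanish-speaking". It is not this trial's sample, and that figure is not labeled primary language.
- Gap g between language groups, in within-group SD. No document gives one, so a range is shown.

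**Formulas.** Between-group variance v = p(1 − p)g², with 0.77 × 0.23 = 0.1771. Share of variance explained R² = v/(1 + v). The adjusted standard error is √(1 − R²) times the unadjusted one. Adjusted power = Φ(2.806/√(1 − R²) − 1.96). The gain is worth 1/(1 − R²) − 1 = v more dyads.

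| g | v | R² | SE ratio | Power, 0.3 SD | Worth in dyads |
|---|---|---|---|---|---|
| none | – | – | 1 | 80.1% | – |
| 0.2 | 0.0071 | 0.007 | 0.996 | 80.4% | +0.7% |
| 0.3 | 0.0159 | 0.016 | 0.992 | 80.7% | +1.6% |
| 0.5 | 0.0443 | 0.042 | 0.979 | 81.8% | +4.4% |
| 0.8 | 0.1133 | 0.102 | 0.948 | 84.2% | +11.3% |

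**Other language mixes.** At g = 0.5, a 50% share gives R² = 0.059 and power 82.4%; a 90% share gives R² = 0.022 and power 81.0%.

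**The CDI, for contrast.** A simulation used 175 per arm, 77% Spanish-speaking, gaps of 0.3 to 0.8 SD, 400 runs per setting and assumed correlations. Adding language to a baseline ANCOVA lowered the standard error by about 0.3% to 3%. On the plan's outcome, with the individual intercept and baseline contribution subtracted, the standard error did not fall (ratio 1.001 to 1.007). Those last standard errors are naive ANOVA values, useful only for comparing models with and without language.

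**The case against.** The strongest reply is that the size is assumed throughout. No document links language to EOWPVT-4 score, the 77% comes from another sample, and at a 0.3 SD gap the gain is about half a point of power. Caregiver primary language is also an imperfect stand-in for what a child hears in a bilingual home, which could lower the variance explained. All of this stands. It limits the size of the gain but does not remove the reason to name the covariate.

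Four stronger readings are tempting and are not supported:
- **That the CDI loses precision too, because it exists in two languages.** Its planned baseline term and individual intercept already absorb most stable differences between children, and the simulation shows little or no further gain. The forms argument does not carry over to the EOWPVT-4 either, since all children take one edition.
- **That the treatment comparison is biased.** Randomization protects it.
- **That the trial is underpowered because of the omission.** The stated 80% already assumes no covariate. Starting from 168 per arm (80% of 630 is 504, or 168 each; power 78.5%) would bring in a separate question about attrition arithmetic. The plan states 175.
- **That chance imbalance in language is a further harm.** At 175 per arm the SD of the difference in Spanish share is √(2 × 0.1771/175) = 0.045. At g = 0.5 this shifts the contrast by 0.5 × 0.045 = 0.0225 SD. Its square, 0.000506, equals 2v/n = 2 × 0.0443/175, so it is the same variance already counted in the table.

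**Conclusion.** The point holds for the EOWPVT-4 only. Its primary analysis has no baseline and no stated covariate, while a plausible predictor is recorded before follow-up. Nothing in the plan is invalid as a result; this is an inexpensive improvement to the analysis.

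On the assumed 77% share and 175 completers per arm, the gain is about 0.6 points of power at a 0.3 SD gap, 1.7 at 0.5 and 4.1 at 0.8. It shrinks toward zero if the gap is small or nearly all families share one language. The "99.9% power to detect a 0.6 SD difference between the community resource arm and ROR only" needs no help from a covariate: 0.6 × √87.5 − 1.96 = 3.65, so power is above 99.9% already.

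**What to change.** In section 6.1, item 3, state that the primary EOWPVT-4 analysis is a linear model (ANCOVA) with treatment and the caregiver's primary language at enrollment (English or Spanish) as fixed effects. Specify the enrollment value, not any language choice made at follow-up, because that choice comes after randomization. Say in advance how a caregiver who names both languages is coded. Child age and sex can then be added to this model in the sensitivity analysis already planned, and the p-value from the primary model should be the one that enters the step-down minP procedure.

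Leave the CDI analysis unchanged in this respect.

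The cost is a sentence or two of SAP text and one degree of freedom. No new data are needed. The downside is that the gain may be negligible if the language gap turns out small.

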When and if COVID-19 guidelines are relaxed, we would like to continue recruitment in person in clinic waiting rooms. Clinicians may continue to refer potential participants to us, as well. We will continue with the same process outlined above to screen the potential participant, explain the study, and provide informed consent. When in person, we will use our written informed consent form. We have an NIH Certificate of Confidentiality, which will be issued automatically, and we have included this language in our consent forms. We will perform our enrollment surveys and give the participant a list of community resources that may help with social support needs.

Participants will be randomly assigned to one of three study arms: Arm 1 Reach Out and Read: The Reach Out and Read model consists of creating literacy rich environments (e.g., children's books present in waiting room), healthcare professionals distributing age and language appropriate children's books, providing anticipatory guidance on shared reading, and modeling dialogical reading which emphasizes responsive and language-rich parent-child interactions.

Arm 2 Reach Out and Read plus outreach text messages: In addition to Reach Out and Read, participants will receive three text messages a week and one follow-up message per month for the study period with scheduled breaks. Messages will be tailored. Tailoring strategies will include personalization and feedback. We will personalize messages based on language preference (English or Spanish), child sex, and optimal timing of messages (morning or evening). For feedback, we will use bidirectional messages once per month. For the once-a-month follow-up message, parents will be asked to respond to a question regarding shared reading in the past week; they will receive a supportive response based on their answer. We will also send a text for birthdays and other child milestones to help build rapport.

Arm 3 ROR + texts + Connecting NJ: In addition to Reach Out and Read and text messages, participants will be referred to Central Jersey Family Health Consortium for Connecting NJ. Our RA will explain Connecting NJ and will email or link the participant to Connecting NJ informational

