materials. We will provide Connecting NJ with basic demographic information about the participant. A case manager from Connecting NJ will then call the participant to assess potential participant needs related to child development, housing insecurity, food insecurity, transportation, financial strain, and problems paying utilities, as is her usual process when she receives referrals from the community and/or clinics. Families in this arm will be referred to Connecting NJ via electronic referral at enrollment. Connecting NJ is based on the national Help Me Grow model and simplifies access to poverty-reducing resources by creating a centralized access point, maintaining an updated data base of resources with existing capacity to support families, and providing case management to ensure families are linked to community resources (e.g., Supplemental Nutrition Assistance Program). Central Jersey Family Health Consortium will share data with us about which resources participants were referred to via a secure platform. We will sign a Data Use Agreement with them (forthcoming).

All participants will receive the standard Reach Out and Read intervention in which healthcare professionals distribute books and model shared reading during well visits to encourage parents to read aloud with their children. Literacy promotion is the pediatric standard of care.

Research materials will consist of:

- (1) Demographic Information and Language Use questionnaire we constructed by adapting questions from the U.S. Census and the Medical Expenditure Panel Survey (MEP) and from our prior experiences in the field. This questionnaire includes a question about English proficiency.
- (2) The Short Assessment of Health Literacy (SAHL-E),¹⁴ a brief assessment of adult health literacy that asks the participant to identify words associated with health-related terms.
- (3) We include two questions in our Discrimination Questionnaire related to racial/ethnic discrimination.
- (4) A survey to assess participant Receipt of Reach Out and Read interventions.
- (5) Language acquisition will be assessed using the Expressive One-Word Picture Vocabulary Test - Fourth Edition (EOWPVT-4) Spanish-Bilingual - Complete.¹⁵ and the MacArthur Bates Communicative Development Inventory (CDI),¹⁶ direct assessments of child language development.
- (6) The Devereux Early Childhood Assessment (DECA),¹⁷ a parent-completed behavior rating scale.

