	(2) Health literacy	Short Assessment of Health Literacy (SAHL)	Enrollment	2.5 minutes
	(3) Discrimination	Discrimination Questionnaire	Enrollment	4 minutes

Process measure	(4) Reach Out and Read Receipt	ROR Receipt Questionnaire	Enrollment, 9 m, 18 m	4 minutes
Primary Outcomes	(5) Language skill acquisition	Expressive One-Word Picture Vocabulary Test - Fourth Edition (EOWPVT-4) Spanish-Bilingual - Complete	18 m	5-20 minutes
		MacArthur Bates CDI	Enrollment, 9 m, 18 m	20 minutes
	(6) Social-emotional skill acquisition	Devereux Early Childhood Assessment (DECA)	Enrollment, 9 m, 18 m	5 minutes
	(7) Shared reading (Parent investment) and parent responsiveness	Modified StimQ Read scale	Enrollment, 9 m, 18 m	5 minutes
		StimQ Parental Verbal Responsiveness	9 m, 18 m	6 minutes
		DialogPR Observation of parent-child interactions	9m, 18 m	4 minutes
	(8) Positive and negative parenting behaviors	Parenting Your Infant, Parenting Your Toddler	Enrollment, 9 m, 18 m	4 minutes
		Parent Discipline Questionnaire	Enrollment, 9 m, 18 m	< 1 minute
Secondary outcomes	(9) Reading attitudes and knowledge	Parent Reading Belief Inventory (PRBI)	9 m, 18 m	3 minutes
	(10) Access to community resources	Adapted Survey of Income and Program Participation (SIPP)	Enrollment, 9 m, 18 m	2 minutes
	(11) Parent-clinician relationship	Modified Physician-Parent Communication Survey	Enrollment, 9 m, 18 m	2 minutes
	(12) Parent stress and wellbeing	Adapted LINK survey	Enrollment, 9 m, 18 m	8 minutes
		Parental Stress Scale	Enrollment, 9 m, 18 m	3 minutes
	(13) Child media use	Modified ScreenQ-I/T 2.0 (Infant/Toddler)	Enrollment, 9 m, 18 m	6 minutes

C. Study Duration

Up to 5 years; participants will be involved up to 2 years.

D. Endpoints

Study participation will conclude upon completion of data collection

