For the mediation analyses in Aim 2, we will examine the extent to which the home literacy environment mediates the effect of the interventions on language skill and social-emotional skill acquisition using the product of coefficients method with each outcome at each post-intervention timepoint individually.³² We will calculate bootstrap bias-corrected confidence intervals ($n=5,000$) to estimate the proportion of treatment effect explained via the home literacy environment. While we expect the effect of the ROR + text messages (arm 2) intervention will mainly operate through the home literacy environment (parent investment) based on our conceptual framework, we expect that the ROR + text + Connecting NJ (arm 3) intervention will also have effects on parenting stress and other responsive parenting interactions (parental verbal responsiveness) through increased access to poverty-reducing community resources accounting for the greater hypothesized impact. We will test this more complex conceptual framework based on an adaptation of the Gershoff model using Structural Equation modeling without latent factors.

For aim 3, the mixed methods approach will allow us to systematically compare data on intervention implementation with the perspectives of parents and clinicians in an ongoing manner. Integration of quantitative and qualitative data will occur at the design, methods, and reporting levels. We will use a convergent design in which we collect quantitative data on key intervention components in the same time frame as we conduct observation (if possible) of study visits.

Parent-child observations will be analyzed by the study team, led by [name]. The observations will be coded according to parent-child interactive behaviors (did expected behaviors occur or not).

Practice and clinician surveys and clinician interviews will be analyzed using qualitative methods to identify changes and adaptations to ROR implementation protocols over time. The evaluation aims to determine what was implemented, how it was implemented, and what changes occurred to implementation over time. We also seek to understand how clinic context affected implementation. These qualitative findings will help inform our quantitative patient-reported outcomes.

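### When the Aim 2 reading mediator and the CDI or DECA outcome come from the same parent, correlated answering can produce a significant indirect effect without true mediation; the plan should name the mediator and lead with EOWPVT-4.

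*Combined protocol and SAP*

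**What the plan says.** Section 6.1 (Analysis, Aim 2) examines the extent to which the "home literacy environment mediates the effect of the interventions on language skill and social-emotional skill acquisition". It uses the product of coefficients, takes each outcome at each post-intervention timepoint separately, and applies bias-corrected bootstrap intervals with 5,000 resamples. It states no covariates, no time ordering and no sensitivity analysis for a shared reporter. The structural equation model for the wider framework has no latent factors, so as written it contains no shared-reporter term.

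No mediator instrument is named. Section 6.1 glosses the home literacy environment as parent investment. The Data Points table (Section 1.3 B) uses that label in the row "Shared reading (Parent investment) and parent responsiveness", which lists the StimQ Read scale first, followed by StimQ verbal responsiveness, DialogPR and the parent-child observation.

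On who reports what, Section 1.6 B says: "The StimQ is a parent-reported measure of the cognitive home environment for children". It says the CDIs "are standardized, parent-reported check-lists that assess language and communication", and it describes the DECA as a parent report. Section 1.3 A, however, groups the CDI with the EOWPVT-4 as "direct assessments of child language development". The EOWPVT-4 is administered by research assistants, at 18 months only (Sections 1.3 B and 1.9 A).

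In the text arms parents receive three messages a week. Once a month, "parents will be asked to respond to a question regarding shared reading in the past week; they will receive a supportive response" (Section 1.3 A, Arm 2). Arm 3 receives texts as well; Arm 1 does not.

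**The concern.** In a product-of-coefficients test, the first path is the arm difference in the mediator. The second is the association of mediator with outcome, given arm. Randomization protects the first path but not the second. If a parent who tends to answer favourably about reading also tends to answer favourably about the child's words and behaviour, the second path is non-zero within every arm, before any text is sent.

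The first path may then come from either of two sources. One is a change in how parents in the text arms report reading. They cannot be unaware of the texts, no masking of parents is described, and they are asked about reading every month. The other is a real rise in reading: Section 1.4 reports that texts improved the home literacy environment in the team's earlier trial and that effects on child outcomes are not known. Either way, H2A could appear supported although reading did not affect the child. Every 9-month child outcome and every social-emotional outcome in Aim 2 is exposed in this way.

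**Working it through.** **The plan's own figure.** Section 6.1 gives no operating characteristic for Aim 2, only 80% power for 0.3 SD with 175 completers per arm. Power = Φ(d·√(n/2) − 1.96) = Φ(0.3 × √87.5 − 1.96) = Φ(2.806 − 1.96) = Φ(0.846) = 80.1%, which reproduces it. The stated 80% completion gives 0.8 × 210 = 168 per arm, where power is 78.5%. Both sample sizes are used below, and the difference does not matter here.

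**Model with no true mediation.** Reported mediator and outcome each have variance 1. A fraction s of each is a common answering factor; the rest is independent. Arm shifts the reported mediator by d SD, and reading has no effect on the child. Then:

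- arm-to-mediator path: a = d
- mediator-to-outcome path given arm: b = s
- false indirect effect: a·b = d·s, for example 0.2 × 0.2 = 0.04 SD; the simulated mean was 0.040

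The values of s and d are assumptions.

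**Hand approximation, 175 per arm.** The indirect effect needs both paths to be clear of zero.

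- Path a: z = d·√(n/2), which is 1.871 at d = 0.2 (chance of exceeding 1.96: 46%) and 2.806 at d = 0.3 (80%).
- Path b: z = s / √[(1 − s²)/(2n − 3)], which is 0.1/√(0.99/347) = 1.87 at s = 0.1 (46%) and 0.2/√(0.96/347) = 3.80 at s = 0.2 (97%).
- Products: about 22% and 37% at s = 0.1 for d = 0.2 and 0.3; about 45% and 77% at s = 0.2.

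**Simulation with bias-corrected bootstrap intervals.** The 175-per-arm run and the first 168-per-arm run below each used 400 trials per cell and 1,000 resamples. The Monte Carlo error is about √(0.5 × 0.5/400) = 2.5 points. The 175-per-arm run counts only intervals wholly above zero.

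| Run | s = 0.1: d = 0.2 / 0.3 | s = 0.2: d = 0.2 / 0.3 |
|---|---|---|
| 175 per arm, mediator shifted | 35% / 46% | 51% / 82% |
| 168 per arm, both reports shifted | 28% / 46% | 49% / 80% |
| 168 per arm, repeat | 29% / 47% | 54% / 81% |

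The bootstrap rejects somewhat more often than the hand approximation, in the same pattern.

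**Each ingredient removed in turn.**

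- Shared factor but no shift: 3% to 4% (175 per arm).
- Mediator shift up to 0.4 SD but no shared factor: at most 4%.
- Both reports shifted by 0.1, 0.2 and 0.3 SD but no shared factor: 1%, 3% and 8% in one run; 5% to 7% in another.
- Mediator alone shifted, against both shifted, at s = 0.2 and d = 0.1, 0.2 and 0.3: 19%, 48% and 80% against 19%, 48% and 82%. Shifting the outcome report adds almost nothing.

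**Possible safeguards.**

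- Adjusting for enrollment values does not remove the problem: 49% to 62% at d = 0.2 and 71% to 90% at d = 0.3 (s = 0.2 to 0.4).
- A null total effect does not flag it. With only the mediator shifted, the total effect was significant in 3% to 8% of trials, and Section 6.1 does not make mediation conditional on it.
- A directly assessed outcome with a parent-reported mediator does remove it: 2% to 5% (d = 0.2 to 0.4, s = 0.2 or 0.4).

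**The case against.** A reader might infer that the monthly question by itself teaches parents to inflate both reports and so manufactures mediation. The calculation does not support that. A shift in both reports without a shared factor leaves the rate at about 7% or less, within simulation error. The false second path comes from correlation already present in parents' answers. Two separate assumptions are needed, and the documents measure neither.

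A reader might also infer that the plan has chosen StimQ Read and excluded the coded observation. It has done neither. The observation sits in the same table row, and StimQ Read is an inference from the shared label. The supportable defect is that the mediator is unspecified.

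It is fair to say that an analysis largely free of this problem is already planned, because mediating each outcome includes the EOWPVT-4. That stands, and it limits the point to CDI and DECA. It is also fair that both Arms 2 and 3 receive texts, so the text-driven route concerns their contrasts with Arm 1 and is weaker for Arm 3 against Arm 2. The process table in Section 1.6 appears to tick bidirectional messages for Arm 3 only. That may be a reproduction fault, and the weekly texts reach Arm 2 in any case.

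Finally, Aim 2 is about examining mechanisms. Counting only trials whose total effect is also significant, with both reports shifted by 0.1, 0.2 or 0.3 SD, the rates fall to 4%, 27% and 66% at s = 0.2 and to 4%, 16% and 34% at s = 0.1. This lowers the figures but does not remove the problem, and the plan sets no such condition.

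**Conclusion.** The concern holds for H2A where a parent-reported mediator is paired with the CDI or DECA, mainly for Arms 2 and 3 against Arm 1. With a 10% to 20% shared factor and a mediator shift of 0.2 to 0.3 SD, about 28% to 81% of trials would show a significant indirect effect with no true mediation. These figures rest on assumed values and on reading StimQ Read as the mediator. They show that the analysis cannot separate mediation from shared answering; they do not show that the bias will occur at that size.

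The documents do not support a claim that Aim 2 as a whole is invalid. Nor do they make observation-to-EOWPVT-4 the only acceptable test: that pairing would leave the social-emotional part of H2A untested, and breaking the shared reporter on the outcome side is already enough.

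**What to change.** In Section 6.1, Aim 2:

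1. Name the mediator instrument.
2. Make the 18-month mediation with EOWPVT-4 as outcome the lead test of the language part of H2A.
3. Report the StimQ-to-CDI and StimQ-to-DECA indirect effects as supportive, and state that they do not by themselves establish H2A.
4. Add the coded observation as an alternative mediator in a sensitivity analysis, including for DECA. State its limits: parents may decline recording after randomization, behaviours are coded only as occurring or not, and there is no enrollment value.

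In Section 1.3 A, describe the CDI as parent-reported, in line with Section 1.6 B.

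This is analysis wording only, since every measure is already collected. The price is that the social-emotional part of H2A and all 9-month mediation rest on supportive evidence only.
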